#### **12.5 Treatment Exposure**

Individual data listings for treatment exposure will be presented for each subject. Treatment exposure will be summarized as extent of exposure to the study drug. Measures of extent of exposure include the total number of doses per subject and compliance. Treatment compliance is defined as the number doses administered per protocol/number of doses prescribed per protocol. Treatment exposure will be summarized using the Safety population by actual treatment.

#### **12.6 Patient Disposition**

Individual data listings for patient disposition will be presented for each patient, including enrollment date, treatment start date, treatment discontinuation date, discontinuation reason, and population flags. The number and percentage of patients entering and discontinuing the study will be presented by randomized treatment group for the double-blind and placebo-controlled 24-week histology cohorts and by enrolled treatment group for the open-label single-blind cohort. The reasons for discontinuation will also be summarized. Patient disposition will be summarized using the ITT population for the double-blind and placebo-controlled 24-week histology cohorts and the All Patients population for the open-label single-blind cohort.

#### **12.7 Protocol Deviations**

Individual data listings for protocol deviations will be presented for each patient. Protocol deviations will be summarized using the ITT population for the double-blind and placebo-controlled 24-week histology cohorts and the All Patients population for the open-label single-blind cohort.

#### **12.8 Demographic Analysis**

Individual data listings for demographic and Baseline characteristics will be presented for each patient. Demographic and Baseline characteristics will be descriptively summarized by randomized treatment group for the double-blind and placebo-controlled 24-week histology

cohorts and by enrolled treatment group for the open-label single-blind cohort. Quantitative and/or categorical summaries will be presented for demographics, medical history, and other Baseline characteristics. Demographic and Baseline characteristics will be summarized using the ITT population for the double-blind and placebo-controlled 24-week histology cohorts and the All Patients population for the open-label single-blind cohort.

## **12.9 Efficacy and Pharmacodynamics**

Individual data listings for efficacy and PD variables will be presented for each patient. Efficacy and PD summaries and analyses will use the Efficacy population.

### **12.9.1 Efficacy and Pharmacodynamic Endpoints**

The primary efficacy endpoint for this study will be the absolute change in liver fat content as measured by MRI-PDFF in patients subjects with histologically confirmed NASH after 12 or 24 weeks of treatment.

#### Secondary Objectives:

- Evaluate the percentage change in absolute liver fat content at EOT.
  - In the open-label single-blind cohort, additional evaluations will be performed at Weeks 6 and 18.
  - In the placebo-controlled 24-week histology cohort, additional evaluations will be performed at Weeks 6, 24, and 30.
- Evaluate the percentage of normalization for liver fat content at EOT.
- Evaluate the change in liver fat content response rate as defined by a  $\geq 5\%$  decrease in absolute liver fat content.
- Evaluate the absolute and percentage changes from Baseline to EOT as well as the percentage of normalization of the following parameters: ALT, AST, triglycerides, bilirubin (total and direct), and GGT. Percentage of normalization will also be investigated for a clinically meaningful threshold for triglycerides.
- Evaluate the absolute and percentage changes from Baseline to EOT of the following:
  - Total cholesterol, HDL-C, LDL-C, triglycerides, and lipoprotein particles
  - FFAs
  - Fasting blood glucose, insulin levels, [REDACTED], and HOMA-IR
  - Pro-C3 and ELF scores (Placebo Controlled 24 Week Histology Cohorts)
  - Body weight, BMI, and waist circumference
  - C4 and serum bile acids
  - Bile-mediated absorption as measured by vitamin D, INR, and fecal fat content
- Evaluate the liver histologic response in Placebo Controlled 24 Week Histology Cohorts
  - Improvement in liver fibrosis by  $\geq 1$  stage by NASH Clinical Research Network (CRN) criteria with no worsening of steatohepatitis

- Resolution of NASH (defined as an NAS score of 0 or 1 for inflammation and 0 for ballooning) with no worsening of fibrosis as determined by the NASH CRN criteria.
- Evaluate the exposure of NGM282 in patients with NASH.
  - In the double-blind and placebo-controlled 24-week histology cohorts, NGM282 exposure will be compared to placebo at 2 hours post-dose at Day 1 and EOT and pre-dose at all on-treatment study visits.
  - In the open-label single-blind cohort, NGM282 exposure will be compared across the dosing groups at 2 hours post-dose at Day 1 and Week 12 and pre-dose at all on-treatment study visits. Additional PK samples will be collected at Baseline and 1, 2, 4, 8, and 12 hours post-dose on Day 1 and Week 6 in a subset of subjects in each dosing group.

Exposure of all doses from both double-blind and open-label single-blind cohorts will be compared to each other as well as to exposure in other study populations treated with NGM282 (Studies [12-0101](#), [13-0102](#), [13-0103](#), [14-0104](#), and [15-0106](#)).

The impact of rosuvastatin administered in response to increases in total cholesterol and LDL-C from NGM282 treatment will be evaluated.

### Exploratory Parameters:

Term	Percentage
GMOs	95
Organic	85
Natural	98
Artificial	75
Organic	80
Natural	95
Artificial	85
Organic	90
Natural	95
Artificial	80

## 12.9.2 Analysis of Primary Endpoint

The analysis of the primary endpoint will be based on the Efficacy population.

The absolute change in liver fat content from Baseline to EOT will be compared between treatment groups using an analysis of covariance (ANCOVA) model with treatment group and diabetic status (double-blind cohort only) as cofactors and Baseline endpoint as a covariate. Least square means with standard errors (SEs), differences in least square means with SE, 95% CIs for the difference in least square means, and corresponding p-values will be presented. Further covariates/cofactors may be included in the modeling depending on the relevance to the endpoint analyzed and will be further described in the SAP.

In cases where the parameters do not follow a normal distribution, a non-parametric approach will be followed to analyze the difference between treatment groups.

The primary analysis for the primary endpoint will be repeated for the Per Protocol population.

### **12.9.3 Analysis of Secondary Endpoints**

The analysis of secondary PD endpoints will be based on the Efficacy population, for all three cohorts separately.

For continuous secondary endpoints the same method of analysis as for the primary endpoint will be followed. Further covariates/cofactors may be included in the modeling depending on the relevance to the endpoint analyzed and will be further described in the SAP.

Categorical secondary endpoints (percentage of normalization) will be analyzed through a chi-square test. The difference between proportions along with 95% CIs for the difference between proportions will be presented by treatment-group comparisons.

The analyses in the open-label single-blind cohorts will be stratified by statin use at Baseline whereas they will be stratified by fibrosis stage in the placebo-controlled 24-week histology cohort. The effect of statin use on lowering LDL cholesterol will also be explored both the open-label single-blind and placebo-controlled 24-week histology cohorts. In addition, sensitivity analyses will be performed to investigate the effect on the efficacy endpoints of statin use in the open-label single-blind cohorts and fibrosis stage on the placebo-controlled 24-week histology cohort.

Comparisons between the 3 cohorts will be performed and further detailed in the SAP.

### **12.9.4 Analysis of Exploratory Endpoints**

The analysis of exploratory endpoints will be based on the Efficacy population.

For continuous exploratory endpoints the same method of analysis as for the primary endpoint will be followed. Further covariates/cofactors may be included in the modeling depending on the relevance to the endpoint analyzed and will be further described in the SAP.

## **12.10 Safety**

Safety and tolerability will be assessed by clinical review of the following parameters: AEs, clinical laboratory tests, physical examination, and vital signs. All safety analyses will be conducted using the safety population.

### **12.10.1 Adverse Events**

AEs, including serious AEs, will be coded using the MedDRA. The number and percentage of subjects experiencing an AE will be summarized for each system organ class (SOC) and preferred term (PT) by treatment group. In addition, AEs will be tabulated according to intensity, causality, and relation to the study drug. Individual data listings for AEs will be presented for each subject.

All AE summaries will be restricted to TEAEs only. TEAEs are defined as AEs that commence on or after the time of start of first study-drug administration. AEs without an onset date or time will be defined as treatment emergent, except if an incomplete date (e.g., month and year) clearly indicates that the event started prior to the start of first administration of study drug or if the AE stop date indicates that the event started or stopped prior to the start of first administration of study drug.

For the summaries of AEs, subjects who experience the same AE (in terms of the MedDRA preferred term) more than once will be counted only once for that event. Separate summaries will be provided for AEs by intensity, causality, and relationship to study drug.

All AEs will be listed. SAEs will be summarized and listed.

### **12.10.2 Clinical Laboratory Evaluations**

The absolute and percentage changes from Baseline to EOT and EOS of total cholesterol, HDL-C, LDL-C, and lipoprotein particles will be analyzed through inferential statistics and will be based on the Safety population.

Observed values and absolute changes from Baseline to EOT and EOS for routine chemical laboratory values will be summarized descriptively at each time point for each treatment group and overall. Shift tables may also be presented for select chemistry and hematology laboratory parameters, as defined in the SAP.

Individual data listings of laboratory results will be presented for each subject. Laboratory values will be compared to normal ranges; out-of-range and clinically significant laboratory values will be identified in the listings.

### **12.10.3 Physical Examinations**

Individual data listings for physical examination results will be presented for each subject.

#### **12.10.4 Vital Signs**

Observed values as well as absolute changes from Baseline will be summarized descriptively for all vital-sign parameters, by time point and treatment group. Individual data listings will be presented for each subject.

#### **12.10.5 Pregnancy Test**

Individual listings for urine and serum pregnancy test data will be presented for each subject.

#### **12.10.6 Electrocardiogram**

Observed values as well as absolute changes from Baseline will be summarized descriptively for all ECG parameters, by time point and treatment group. Individual data listings will be presented for each subject.

#### **12.10.7 Injection-Site Reactions**

Frequency tabulations of ISR results will be presented at each time point by treatment group.

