Number of Patients:	Approximately 75 patients (25 per treatment group) will be randomized in the double-blind cohort. Up to 100 additional patients (25 per treatment group) will be enrolled in the open-label single-blind cohort. Approximately 75 additional subjects (50 active, 25 placebo) will be enrolled in the placebo-controlled 24-week cohort.
Number of Study Sites:	Double-blind cohort: ~20 sites worldwide Open-label single-blind cohort: ~6–8 U.S. sites Placebo-controlled 24-week histology cohort : ~10 U.S. sites
Test Product(s), Dose, and Mode of Administration:	For the double-blind cohort, the NGM282 final product will be supplied in pre-filled syringes intended to deliver 0.3 mL (3 mg) or 0.6 mL (6 mg) for SC injection. Placebo will be provided in volume-matched syringes (0.3 mL and 0.6 mL). For the open-label cohort, NGM282 final product will be supplied in pre-filled syringes intended to deliver 0.3 mL (0.3 mg, 1 mg, and 3 mg) for SC injection. For the placebo-controlled 24-week histology cohort, NGM282 final product will be supplied in pre-filled syringes intended to deliver 0.3 mL (1 mg) dose for SC injection. All subjects will be instructed to dose NGM282 each morning and to skip the dose if it is past 12:00 noon and administer the next dose as planned the following morning.  The open-label single-blind and placebo-controlled 24-week histology cohorts will also include treatment with rosuvastatin for subjects meeting pre-specified LDL-C criteria. Study-labeled rosuvastatin 20-mg tablets will be supplied in order to deliver either 20 mg or 40 mg total daily doses as outlined in Section 10.4 to manage possible LDL-C increase during NGM282 treatment.  The placebo-controlled 24-week histology cohort only will also include treatment with ezetimibe co-therapy that will be prescribed by the Investigator when subjects have not achieved an adequate LDL-C response or when subjects are unable to tolerate rosuvastatin. Ezetimibe is formulated as 10 mg tablets and can be administered with or without food at the same time as rosuvastatin and NGM282 or placebo

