has demonstrated a dose-dependent decrease of Cyp7a1 levels. Consistent with reduction in Cyp7a1 levels, serum C4 levels were also reduced in the 28-day monkey toxicology study ([Study 11-TX-NGM282-1002](#)) and 26-week toxicology study in monkeys ([Study 13-TX-NGM282-1004](#)). Significant reductions in serum C4 levels were also observed after administration of NGM282 in normal volunteers ([Study 12-0101](#)).

NGM282 has also been evaluated in two distinct animal models of NASH. Adeno-associated virus (AAV)-mediated delivery of NGM282 transgenes into FXR-deficient mice demonstrated improvement in the histologic, biochemical, and fibrogenic biomarkers associated with NASH-related hepatic injury (Study 13-PD-NGM282-1007). Similarly, AAV administration of NGM282 in the STAMTM model of NASH in mice showed a significant reduction in steatosis, inflammation, ballooning, and overall body weight versus placebo (data on file).

The safety, tolerability, pharmacokinetics (PK), and pharmacodynamics (PD) of NGM282 have been studied in a blinded, placebo-controlled, single-ascending-dose (SAD)/multiple-ascending-dose (MAD) study in normal subjects ([Study 12-0101](#)). NGM282 or placebo was administered to 119 normal subjects as a daily SC injection in escalating doses of 0.1–30 mg in the SAD module and 0.1–20 mg in the MAD module. Multiple-dose PK were consistent with single-dose PK parameters, with no evidence of drug accumulation. NGM282 was safe and well tolerated with no serious adverse events (SAEs) or clinically relevant laboratory abnormalities. Mild to moderate injection-site reactions (ISRs) were the most common drug-related adverse events (AEs), observed mainly with higher doses and larger injection volumes. NGM282 had a favorable safety profile and highly predictable PK that support once-daily dosing.

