The selection of the 0.3, 1, 3, and 6 mg doses is further supported by the efficacy, safety, and tolerability observed in the T2D study in which NGM282 doses of 2, 5, or 10 mg were evaluated. The T2D study patients represent a population similar to the NASH population expected to be enrolled in the NASH Phase 2 study. In patients with T2D, doses > 2 mg are associated with greater decreases in body weight, fasting blood glucose, triglycerides, HDL, and ALT, all of which are parameters associated with potential therapeutic activity in NASH. The subsequent decreases in LDL at Day 28 after initial increases at Day 14 are greater with doses > 2 mg. A trend toward increased frequency and severity of GI symptoms and ISRs in patients treated with 10 mg was noted; therefore, lower doses were selected for tolerability. Lastly, bile acid synthesis as measured by suppression of C4 levels is greatest at doses of 3 mg based on the data from the Phase 1 normal volunteer study. Furthermore, C4 was suppressed by > 95% in T2D patients treated with the 2- and 5-mg doses of NGM282. Based on the above data, the selected doses should allow a balance of optimizing biologic activity versus safety and tolerability in the studied population.

The selection of the lower doses (0.3 mg and 1 mg) for study in the open-label single-blind cohort was based on the robust results of the double-blind cohort demonstrating comparable improvements in the non-invasive markers of NASH at 3 mg and 6 mg, with improved tolerability with the 3 mg dose. Subjects enrolled in the open-label single-blind cohort received 0.3 mg or 1 mg for 12 weeks in order to establish a minimally effective dose, based on non-invasive measures of liver fat, inflammation, and fibrosis. Additionally, based on the rapidity of the treatment effect demonstrated with 3 mg and 6 mg, [REDACTED]

[REDACTED] This demonstrated significant improvement in both NAS and fibrosis scores with 3 mg for 12 weeks. In order to assess the histologic response and utility of 1 mg, a 12-week biopsy dosing group (Group 4) is ongoing.

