For the double-blind cohort, dose reductions will be allowed on a case by case basis for subjects receiving 6 mg or matched 6 mg placebo for safety or tolerability, but must be approved by the Medical Monitor. If approved, the subject will be decreased to 3 mg or the matched 3 mg placebo to be aligned with whether they were initially receiving active drug or placebo prior to the dose reduction. Subjects receiving 3 mg or matched 3 mg placebo will not be allowed to dose-reduce during the study period.

For the open-label single-blind cohort, no dose reductions will be allowed.

For the placebo-controlled 24-week histology cohort **no dose reductions** will be allowed. Additionally, ALT, AST, and all lipid laboratory results are blinded starting with Week 2 onward. The Medical Monitor will be reviewing and monitoring all laboratory results and if any of the liver related testing parameters are observed, investigators will be notified immediately to discuss further evaluation.

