## 12.1 Sample Size

For the double-blind cohort, a sample size of 75 subjects was selected (25 subjects per treatment arm).

Allowing for a dropout rate of 10% the following sample-size sensitivity calculations were based on a minimum number of 22 subjects per treatment group completing the trial.

A 5% difference in total liver fat content is the minimal appreciable difference that would be considered clinically relevant between the active treatment arms and the placebo treatment group. If the NGM282 3-mg and 6-mg groups are assumed to have at least a 6% reduction in liver fat when compared to Baseline along with a reduction of 1% or less from Baseline in the placebo group, with a 5% level of significance, the following illustrates sample-size

power calculations based on varying common standard deviations to achieve an overall (overall F-test) statistically significant treatment effect:

Method	Mean Absolute Change from Baseline			Common SD	Effect Size	Power
	NGM282 6 mg	NGM282 3 mg	Placebo			
One-way analysis of variance (equal n's)	6%	6%	1%	8%	0.0868	54%
	6%	6%	1%	7%	0.1134	66%
	6%	6%	1%	6%	0.1543	80%
	6%	6%	1%	5%	0.2222	92%

SD = standard deviation.

A maximum sample size of 100 subjects was selected (with a minimum of 15 subjects per treatment arm, up to a maximum of 25 subjects per treatment arm) for the single-blind cohort design.

The sample size for the open-label single-blind cohort was not based on a formal sample-size calculation. Instead, it was based on the results of the interim analysis that was conducted when ~15 subjects per arm had completed 12 weeks of treatment. Although the results of this interim analysis are still blinded, the magnitude of the treatment differences observed indicate that a sample size of 15–20 subjects per treatment arm is sufficient to give an initial indication of efficacy for further exploration.

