## 12.2 Randomization and Enrollment

For the double-blind cohort, at Day 1 all eligible subjects will be randomized via IWRs to one of the three treatment arms (NGM282 3 mg, NGM282 6 mg, or placebo) in a 1:1:1 ratio. The proportion of subjects with diabetes (categorized on a dichotomous scale) will be balanced across the three groups to ensure an even distribution across the three groups.

Diabetes status for balancing (“no diabetes” or “diabetes”), will be based on medical history, Screening labs, current medications, and clinical assessments.

The single-blind cohort is not randomized. Subjects will initially be enrolled sequentially into dosing Group 1 and enrollment will be continuous within and between each dosing groups. Sequencing of the dosing Groups 2 and 3 will be based on PD and safety parameters from dosing Group 1 and may run in parallel to each other. A fourth optional dosing group may be conducted based on the safety/tolerability, imaging data and histology (dosing Group 3 only) data from the prior 3 dosing groups. Dosing Group 4 will be initiated only after all subjects in Cohort 3 have been enrolled and a minimum of 10 subjects have completed 12 weeks of treatment in order to do a preliminary review of key data. Dosing group sequence and individual subject treatment assignment will be blinded only study subjects throughout the study period.

For the placebo-controlled 24-week histology cohort, at Day 1 all eligible subjects will be randomized via IWRS to one of the two treatment arms (NGM282 1 mg or placebo) in a 2:1 ratio. The Sponsor, study sites, and subjects will be blinded to treatment assignment. The randomization schedule will be stratified by subject’s fibrosis stage 2 or 3 based on the screening qualification liver biopsy.

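### Double-blind cohort: injection-site reactions are tabulated against one placebo group that mixes 0.3 mL and 0.6 mL injections, so the volume-matched control goes unused.

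*Protocol*

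**What the plan says.** **Volumes.** The protocol Synopsis (test product entry) describes NGM282 syringes for the double-blind cohort as "intended to deliver 0.3 mL (3 mg) or 0.6 mL (6 mg) for SC injection". On the control it says: "Placebo will be provided in volume-matched syringes (0.3 mL and 0.6 mL".

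**Arms.** Section 12.2 randomizes to "one of the three treatment arms (NGM282 3 mg, NGM282 6 mg, or placebo) in a 1:1:1 ratio". Placebo is therefore one arm, and Section 12.1 plans 25 subjects per arm. No section states how the placebo subjects are divided between the two volumes.

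**Reactions and volume.** Section 5.1.3 reports that mild to moderate reactions in the Phase 1 study were "observed mainly with higher doses and larger injection volumes". It gives no rates.

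**Analysis.** Section 12.10.7 reads: "Frequency tabulations of ISR results will be presented at each time point by treatment group". Section 12.10.1 likewise summarizes adverse events by treatment group. Neither splits placebo by volume.

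**Volume changes.** Section 8.2 allows case-by-case dose reduction from 6 mg or its matched placebo: "the subject will be decreased to 3 mg or the matched 3 mg placebo". Placebo volume is thus a recorded distinction, and it can change during the study.

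**SAP.** Section 2 of the supplied SAP limits it to the 24-week histology cohort and says that each phase has its own plan.

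**The concern.** A volume-matched placebo lets each dose be compared with an injection that differs only in drug content. The planned table does not use it. It puts 3 mg beside a placebo group that is partly 0.6 mL, and 6 mg beside one that is partly 0.3 mL. If volume matters, the two comparisons are wrong in opposite directions.

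What is at stake is how the injection-site profile of the two doses is read. Section 5.4 gives as part of the reason for studying lower doses that the double-blind cohort showed comparable activity at 3 mg and 6 mg, "with improved tolerability with the 3 mg dose". Whether more reactions at 6 mg come from the drug or from the larger injection has different implications for the product. The contrast of 0.3 mL with 0.6 mL placebo is the only evidence inside this cohort that can separate the two.

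**Working it through.** The documents give no reaction rate by volume, so there is no stated figure to reproduce. The error can be written out exactly.

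**Inputs from the protocol:** 3 mg = 0.3 mL and 6 mg = 0.6 mL (Synopsis); placebo in both volumes (Synopsis, Section 8.2); 25 subjects per arm (Section 12.1).

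**Inputs assumed:** share w of placebo subjects on 0.6 mL, 1/3 to 2/3; volume effect V = p(0.6) - p(0.3), 10 to 30 percentage points, where p is the reaction risk on placebo at that volume.

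**Error from the mixed placebo group.** Let d3 and d6 be the risk that the drug itself adds at 3 mg and 6 mg.

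- Mixed placebo = (1-w)·p(0.3) + w·p(0.6) = p(0.3) + wV
- 3 mg minus mixed placebo = d3 - wV
- 6 mg minus mixed placebo = d6 + (1-w)V
- Matched comparisons: 3 mg minus 0.3 mL placebo = d3; 6 mg minus 0.6 mL placebo = d6, for any w

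Error in percentage points (3 mg / 6 mg):

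| w | V = 10 | V = 20 | V = 30 |
|---|---|---|---|
| 1/3 | -3.3 / +6.7 | -6.7 / +13.3 | -10 / +20 |
| 1/2 | -5 / +5 | -10 / +10 | -15 / +15 |
| 2/3 | -6.7 / +3.3 | -13.3 / +6.7 | -20 / +10 |

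For example, take no drug effect, w = 1/2, and assumed risks of 10% at 0.3 mL and 30% at 0.6 mL. Mixed placebo is (10 + 30)/2 = 20%. The table then suggests -10 points at 3 mg and +10 points at 6 mg, where the matched differences are both 0.

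**The 6 mg versus 3 mg difference.** Subtracting the two mixed comparisons gives (d6 - d3) + V. The share w cancels, so this gradient contains all of V whatever is done with placebo. It comes from dose and volume moving together in the active arms.

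**Precision of the matched comparison**, with an even split (12.5 placebo subjects per volume, an assumption):

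- At equal risks the ratio of standard errors is sqrt[(1/25 + 1/12.5)/(1/25 + 1/25)] = sqrt(1.5) = 1.22.
- With unequal risks, the 95% half-width for 6 mg versus placebo goes from 21.0 to 27.2 points (risks 10%/20%), 23.8 to 31.1 (10%/30%) and 27.1 to 33.9 (20%/50%). The ratios are 1.29, 1.31 and 1.25, so the interval is about 25% to 31% wider.

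**The case against.** **The SAP for this cohort was not available.** That placebo is pooled follows from tabulation by treatment group and from placebo being one arm; no section says it outright. The separate plan may split it. This stands as a limit, although the protocol does not require a split.

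**A reader might infer that pooling turns a volume effect into a false dose gradient.** The documents do not support that. The gradient between 6 mg and 3 mg is the same with or without a placebo column, because dose and volume are aliased by design. Pooling only hides the contrast that could help separate them. Since 6 mg is supplied only as 0.6 mL, volume-related reactions are also part of that product's actual tolerability.

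**A reader might infer that volume explains the reactions.** Section 5.1.3 names dose and volume together and separates neither. Section 5.4 reports fewer reactions at 1 mg than at 3 mg, and the Synopsis gives both as 0.3 mL, so a true dose effect may exist as well.

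**A reader might infer that dose selection was distorted.** Section 5.4 speaks of tolerability at 3 mg without mentioning injection-site reactions. The later choice of 1 mg compared two doses at the same volume.

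**The output is descriptive.** The Synopsis limits non-lipid safety endpoints to descriptive analysis, and Section 12.10.7 plans frequencies without differences or tests. Each arm's own rate is correct; only the comparison a reader draws with placebo can mislead. This lowers the importance of the point but does not answer it, since showing placebo beside active invites that comparison.

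**Conclusion.** The point holds in a limited form. As the protocol is written, the double-blind injection-site tables do not use the volume-matched control that the design provides. If volume affects risk, comparison with placebo understates the drug's contribution at 3 mg by wV and overstates it at 6 mg by (1-w)V. That is about 3 to 20 points each over the assumed ranges, and zero if volume has no effect.

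The size rests on assumed values of w and V, and the point rests on the unseen double-blind SAP not already splitting placebo. It does not reach the 24-week cohort, where 1 mg and its volume-matched placebo use 0.3 mL (Synopsis and Section 10.1.1). It is a minor, cheap improvement.

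**What to change.** For the double-blind cohort, in Section 12.10.7 and for injection-site adverse events in Section 12.10.1:

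- Show placebo by injection volume (0.3 mL, 0.6 mL) as well as overall.
- Set 3 mg beside 0.3 mL placebo and 6 mg beside 0.6 mL placebo.
- Classify subjects who change syringe volume under Section 8.2 by the volume in use at each assessment. Grouping by actual treatment received (Section 12.4.3) does not settle this for placebo subjects, because both volumes are placebo.
- State how many placebo subjects were allocated to each volume.

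The cost is two more columns and one classification rule, with no new data. The downside is precision. An even split leaves about 12 to 13 placebo subjects per volume, so matched intervals are about 22% wider at equal risks and, in the cases shown, 25% to 31% wider for 6 mg when risks differ. The overall placebo column stays available, and the output should still be presented as descriptive.
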